12.4 MedDRA algorithmic approach to anaphylaxis

[figure not shown]
The SMQ Anaphylactic reaction consists of three parts:

- A **narrow search** containing PTs that represent core anaphylactic reaction terms

- A **broad search** that contains additional terms that are added to those included in the narrow search. These additional terms are signs and symptoms possibly indicative of anaphylactic reaction and categorized in B, C or D

- Cat B

- Cat C

 ^{PT} _C Allergic oedema	 ^{PT} _C Pruritus
 ^{PT} _C Angioedema	 ^{PT} _C Pruritus allergic
 ^{PT} _C Erythema	 ^{PT} _C Pruritus generalised
 ^{PT} _C Eye oedema	 ^{PT} _C Rash
 ^{PT} _C Eye pruritus	 ^{PT} _C Rash erythematous
 ^{PT} _C Eye swelling	 ^{PT} _C Rash generalised
 ^{PT} _C Eyelid oedema	 ^{PT} _C Rash pruritic
 ^{PT} _C Face oedema	 ^{PT} _C Skin swelling
 ^{PT} _C Flushing	 ^{PT} _C Swelling
 ^{PT} _C Generalised erythema	 ^{PT} _C Swelling face
 ^{PT} _C Injection site urticaria	 ^{PT} _C Urticaria
 ^{PT} _C Lip oedema	 ^{PT} _C Urticaria papular
 ^{PT} _C Lip swelling	
 ^{PT} _C Nodular rash	
 ^{PT} _C Ocular hyperaemia	
 ^{PT} _C Oedema	
 ^{PT} _C Periorbital oedema	

- Cat D

 ^{PT} _D Blood pressure decreased
 ^{PT} _D Blood pressure diastolic decreased
 ^{PT} _D Blood pressure systolic decreased
 ^{PT} _D Cardiac arrest
 ^{PT} _D Cardio-respiratory arrest
 ^{PT} _D Cardiovascular insufficiency
 ^{PT} _D Diastolic hypotension
 ^{PT} _D Hypotension

- An **algorithmic approach** which combines a number of anaphylactic reaction symptoms in order to increase specificity. A case must include one of the following where both occur on either the same day as when an injection was administered or one day after, and for scenarios where two events must have been reported, both events must have occurred within one day of each other:
 - A narrow term or a term from Category A;
 - A term from Category B - (Upper Airway/Respiratory) AND a term from Category C - (Angioedema/Urticaria/Pruritus/Flush);
 - A term from Category D - (Cardiovascular/Hypotension) AND [a term from Category B - (Upper Airway/Respiratory) OR a term from Category C - (Angioedema/Urticaria/Pruritus/Flush)]
- Hypersensitivity events will be identified using the “Hypersensitivity (SMQ)”. All TEAEs which code to a PT included in the Scope=Narrow search will be included.

12.5 COVID-19 data collection

For study visits impacted by COVID-19, additional data will be collected on a separate dedicated eCRF page.

The following information will be reported:

- Specification of the impacted visit (eg, Visit 5)
- Date of the impacted visit

- Category of the impact (multiple categories may apply to the same visit)
 - Visit not done
 - Visit performed out of window
 - Home visit
 - Visit performed by video call
 - Visit performed by telephone
 - Investigational product shipped to study participant
 - Home administration of investigational product by participant or caregiver
 - Home administration of investigational product by a healthcare professional
 - Missed study drug administration/dispensation
 - Temporary discontinuation of study drug
 - Permanent discontinuation of study drug
 - Termination of study participation
 - Other
- Relationship to COVID-19
 - Confirmed COVID-19 infection
 - Suspected COVID-19 infection
 - General circumstances around COVID-19 without infection
 - Other

A narrative of the event will also be collected.

This document cannot be used to support any marketing authorization application and any extensions or variations thereof.

13 AMENDMENTS TO THE STATISTICAL ANALYSIS PLAN

13.1 Amendment 1

13.1.1 Rationale for the amendment

The main objective of this SAP amendment is to incorporate relevant updates based on Protocol Amendment 2, dated 09 Mar 2018 and Protocol Amendment 3, dated 06 Feb 2020. Additional details and modifications have been made throughout the document in order to align with the most recent bimekizumab program conventions.

13.1.2 Modifications and changes

The following modifications and changes have been made:

- Efficacy measurements at the SFU visit have been removed from the list of assessments for the other efficacy endpoints ([Section 2.2.2.3](#)).
- Key inclusion criteria have been removed from the SAP as these are available in the final protocol and not relevant to the analyses described within the SAP
- Change from AS0009 EV for safety variables will no longer be presented, since the EV assessment is made after 36 or 48 weeks of bimekizumab treatment and there is unlikely to be any further important change.
- Change from AS0008 Baseline and from AS0009 EV for laboratory parameters (with the exception of CRP) will not be presented, due to a change in laboratory vendor between AS0008 and AS0009. Laboratory Baseline is defined as the earliest value in AS0009 at or prior to AS0009 Week 12.
- Summaries of ASAS40, ASAS20 and ASAS5/6 response at each post-AS0008 Baseline visit in AS0008 through to AS0009 Week 208 have been added for subjects who were responders at AS0008 Week 12. These summaries will be used to assess maintenance of response.
- The relative day will now be calculated twice, once relative to the start of study medication in AS0008 and once relative to the start of study medication in AS0009.
- A definition of the dosing period has been added.
- Baseline values (with the exception of AS0009-Laboratory Baseline values) will now be taken directly from the AS0008 database, and not re-derived.
- The previous version of the SAP stated that ET visits would be mapped to a scheduled site visit if they fell on the scheduled date for that visit. This has been updated to say that they will be mapped to a scheduled visit if they fall within the protocol-defined visit window for that visit, unless there is an existing scheduled site visit in that window, in which case they will be mapped to the next scheduled site visit. Unscheduled visits will now also mapped to scheduled visits if they fall within the protocol-defined window for that visit, unless there is already a scheduled site visit or ET visit in that window. The wording has been clarified regarding unscheduled assessments performed at specific time points.
- The definition of the sub-populations for the SS has been clarified to be based on concomitant rescue medications only.

- Sub-populations of the SS are used to report only TEAEs, serious TEAEs, AE Overview and Exposure rather than all primary and secondary safety variables.
- Summaries based on sub-populations of the SS will only be reported in the event that the number of subjects receiving rescue medication is $\geq 10\%$ of the total number of subjects in the SS.
- The protocol and previous version of the SAP describe the FAS as consisting of all enrolled subjects who receive at least 1 dose of IMP and have a valid measurement for at least 1 efficacy variable at AS0009 study entry. This has been updated to include all subjects in the ES who received at least one dose of study medication in AS0009 and have a valid measurement for at least one efficacy variable after AS0009 EV in order to identify subjects who have had assessments during AS0009.
- Summaries by randomized treatment in AS0008 will not be produced, as subjects will have been on a constant dose of bimekizumab 160mg or 320mg for at least 36 weeks prior to AS0009 entry. Maintenance of response displays will be split by treatment sequence across AS0008 and AS0009. Safety displays using AS0008 information will incorporate exposure in AS0008.
- The protocol defines subgroups based on ‘Concomitant non-steroidal anti-inflammatory drug (NSAID) status at AS0009 entry. This has been updated to ‘Concomitant NSAID status at start of AS0008’.
- The rules for NRI and MI for missing efficacy data have been clarified to state that imputations will only be performed for subjects in the FAS for AS0009. In addition the SAP has been updated to state that for NRI, the imputation will be re-derived at the AS0009 EV instead of using the AS0008 Week 48 imputed value; this is due to slight differences in the derivation rules for some endpoints between the AS0008 and AS0009 SAPs.
- The MI procedures have been updated for all endpoints to use OC data from both AS0008 and AS0009 studies such that missing data across both studies will be imputed. Thus, the procedure will estimate an imputation model at each post-AS0008 Baseline visit where efficacy variables are collected. The covariate for AS0009 EV has therefore been deleted from the model.
- The endpoints/components for which MI will be performed have been clarified in the section on handling missing data for the efficacy analyses.
- The presentation of CRP data following MI has been updated to use the geometric mean and 95% CI for the geometric mean
- The handling of missing data for AEs and concomitant medications has been updated to clarify the rules in the presence of a partial start date and a known end date.
- For summaries based on MI of missing data, the covariates in the MI model will no longer include disease duration and concomitant NSAID status.
- The seed used for all MI procedures has been updated to 2017.

- A summary of study medication discontinuation and a listing of subjects excluded from at least one analysis set have been added.
- Methods for calculating total days on study medication have been added to the SAP
- Tables and listings presenting the impact of COVID-19 on the study data collection have been added
- The listing of lifestyle data has been removed, as this data is not generally collected in AS0009. Lifestyle data may be collected for PDILI cases, and this data will be listed.
- The categories and rules for identifying rescue medications have been updated
- Efficacy data collected after a subject has used a prohibited medication will no longer be treated as missing since the primary purpose of this study is to assess safety.
- Compliance categories have been updated from <=80% and >80% to <=75% and > 75% to match the overall program conventions for bimekizumab.
- Sensitivity analyses based on OC data were restricted to ASAS40, 20, ASAS5/6 and BASDAI. Additional sensitivity analyses based on MI of component scores were added for ASAS40 and ASAS20 response variables.
- The data handling rules for ASAS response derivations have been updated and clarified to match the overall program conventions for bimekizumab
- Summaries of MASES were restricted to subjects with enthesitis (MASES > 0) at AS0008 Baseline
- CRP values below the LLOQ will now be set to half LLOQ (0.08mg/L) prior to reporting (rules for calculation of ASDAS-CRP use different conventions for values that are below the LLOQ).
- Plots of geometric mean bimekizumab plasma concentration versus time by treatment group and cumulative ADAb status have been added based on ADAb status in AS0008 and AS0009.
- ADAb status categories have been redefined and appropriate plots and summaries have been added based on the most recent bimekizumab program conventions.
- Summaries of all TEAEs and serious TEAEs in AS0008 and AS0009 combined, a corresponding AE overview table and a table of exposure across AS0008 and AS0009 have been added.
 - Summaries have been added for fatal TEAEs; TEAEs leading to permanent withdrawal of study medication; serious TEAEs by maximum relationship and fatal TEAEs by maximum relationship. The Adverse Drug Reaction summary has been removed. A listing of Hospital/ER visits has been added.
- A summary of TEAEs by descending frequency of PT has been added
- A summary of TEAEs in AS0009 and ongoing TEAEs from AS0008 has been added

- Tables and listings have been added to evaluate the effect of COVID-19 on reporting of TEAEs
- The summaries and listings for AEs of special interest have been updated to match more recent guidelines.
- Further clarification has been added to the definitions of EAIR and EAER.
- Summaries and shift tables of subjects experiencing a given CTCAE grade for selected laboratory parameters have been added.
- Summaries presenting outliers for QTcB and QTcB have been added
- A listing of ECG findings has been added
- Body weight and BMI have been added to the listing and summary table for vital signs variables
- Physical examination data will no longer be listed as this data is not collected.
- A listing of healthcare provider consultations listing has been added.
- A listing of comments has been added.
- A listing of procedure history has been added.
- The appendices containing the copies of the individual questionnaires have been removed

13.2 Amendment 2

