3.3 Other objectives

The other objectives are:

- To assess the impact on patient-reported quality of life
- To assess the impact on enthesitis
- To assess the plasma concentrations of bimekizumab
- To assess the immunogenicity of bimekizumab

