4.3.2 Efficacy variables

Other efficacy variables are listed below and will be evaluated at scheduled visits in accordance with the schedules of assessments in [Table 5–1](#) and [Table 5–2](#).

- ASAS40 response
- ASAS20 response
- ASAS5/6 response
- ASAS partial remission
- Change from Baseline of AS0008 in Ankylosing Spondylitis Disease Activity Score-C-reactive protein (ASDAS-CRP)
- Ankylosing Spondylitis Disease Activity Score Inactive Disease (ASDAS-ID)
- Change from Baseline of AS0008 in Bath Ankylosing Spondylitis Disease Activity Index (BASDAI)
- Change from Baseline of AS0008 in Bath Ankylosing Spondylitis Functional Index (BASFI)
- Change from Baseline of AS0008 in Bath Ankylosing Spondylitis Metrology Index (BASMI)
- Change from Baseline of AS0008 in the MASES Index
- Change from Baseline of AS0008 in Patient's Global Assessment of Disease Activity (PGADA)
- Change from Baseline of AS0008 in total and nocturnal spinal pain
- Change from Baseline of AS0008 in Short Form 36-item Health Survey (SF-36)
- Change from Baseline of AS0008 in Ankylosing Spondylitis Quality of Life (ASQoL)

- Change from Baseline of AS0008 in the Hospital Anxiety and Depression Scale-Anxiety (HADS-A) and Hospital Anxiety and Depression Scale-Depression (HADS-D) scores
- Depression and anxiety status “normal” as defined by HADS-D and HADS-A <8

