13.4 Planned efficacy analyses

Secondary and other efficacy variables will be summarized for all subjects in the FAS; efficacy analyses will be performed over the 208 weeks (4 years).

Responder variables (eg, ASAS20 response) will be derived relative to Baseline of AS0008, and summarized descriptively. Percentages will be summarized descriptively by visit, by randomized treatment group, and by treatment group at completion of the lead-in study.

Change from Baseline of AS0008 of all continuous variables will be summarized descriptively by visit, by randomized treatment group, and by treatment group at completion of the lead-in study.

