 - For MASES the MI model will be restricted to subjects with a MASES score > 0 at AS0008 Baseline. Subjects with a MASES score of zero at AS0008 Baseline will be excluded prior to performing the procedure outlined below.
- PGADA
- TNSP
- SF-36
 - For SF-36 this will be performed for the Physical Component Summary score (PCS) and Mental Component Summary score (MCS) and for each of the 8 domain scores (Physical Functioning, Role Physical, General Health, Bodily Pain, Vitality, Social Functioning, Role Emotional and Mental Health).
- ASQoL
- HADS-A and HADS-D
 - Incidence of normal HADS-A and HADS-D scores (defined as having HADS-D<8 and HADS-A<8 at the same visit) will be derived at each visit using the values for HADS-A and HADS-D obtained after MI
- CRP
 - Note that for CRP as a standalone endpoint the rules for handling measurements that are below the limit of quantification should be followed as per [Section 8.1.12](#). Thus, if any

imputed values are <0.16mg/L these will be replaced with 0.08mg/L prior to any subsequent reporting.

The missing absolute value (not the change from baseline) will be replaced by one of a set of plausible values, where each value is a Bayesian draw from the conditional distribution of the missing data given the observed data. The basic assumption in MI is that the underlying missing data mechanism is ignorable, e.g. the missing data are missing at random.

All MI procedures will be performed using data from both AS0008 and AS0009 such that missing data across both studies will be imputed. Any previous MI or last observation carried forward (LOCF) (or other e.g., next observation carried backward) imputation performed in AS0008 will not be considered for AS0009 such that the procedure will use OC data only across both studies.

As the AS0008 Week 48 time point is synonymous with the AS0009 EV time point, this will be incorporated once only into the model.

The SAS® PROC MI procedure will be used for the imputation.

The MI consists of 3 steps:

- The missing data are imputed m times to create m complete datasets.
- The m datasets are summarized.
- The results of the m summaries are combined into a single result.

The MI method will be applied as follows:

Step 1

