8 EFFICACY ANALYSES

Missing efficacy data will be imputed as described in [Section 4.2.1](#) prior to reporting. As a sensitivity analysis, summaries will be repeated based on non-imputed (OC) data for the following variables:

- ASAS40 response relative to AS0008 Baseline at each visit in AS0009.
- ASAS20 response relative to AS0008 Baseline at each visit in AS0009.
- ASAS 5/6 response relative to AS0008 Baseline at each visit in AS0009.
- Change from AS0008 Baseline in BASDAI at each visit in AS0009.

A further sensitivity analysis will be performed for ASAS40 and ASAS20 response relative to AS0008 Baseline. The response endpoint will be re-derived and summarized based on the mean value (across multiple imputations) of the individual component scores after imputation for missing data.

Efficacy variables will be summarized and listed for the FAS. Summaries of MASES will be restricted to subjects with a MASES >0 at AS0008 Baseline. Maintenance of response summaries will be restricted to subjects who achieved a response at AS0008 Week 12 for the specific endpoint (where the response at AS0008 Week 12 is taken directly from the AS0008 datasets).

Responder variables (e.g. ASAS40 response) will be derived relative to the AS0008 Baseline and summarized using n and percentage at each visit, by treatment group at completion of AS0008 and overall.

Maintenance of response will be assessed for ASAS40, ASAS20 and ASAS5/6. The responses will be derived relative to AS0008 Baseline and summarized using n and percentage at each post-AS0008 Baseline visit, by treatment sequence across AS0008 and AS0009. These summaries will therefore include AS0008 Week 1, 2, 4, 8 12, 16, 24, and 36 and AS0009 EV (AS0008 Week 48), Week 12, 24, 36, 48, 60, 72, 84, 96, 108, 120, 132, 144, 156, 168, 180, 192, 204, and Week 208. AS0008 Week 1 and 2 are not applicable for ASAS5/6 response.

Absolute and change from AS0008 Baseline for all continuous efficacy variables will be summarized descriptively by visit, by treatment group at completion of AS0008 and overall.

Any data collected at the SFU visit will be excluded from all efficacy summaries; this data will be included in the listings only.

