8.1.6 Maastricht Ankylosing Spondylitis Enthesitis Index

The MASES Index comprises 13 items (bilateral costochondral 1, costochondral 7, anterior superior iliac spine, posterior iliac spine, iliac crest and proximal insertion of the Achilles tendon sites, and the fifth lumbar vertebral body spinous process) (Heuft-Dorenbosch et al, 2003) each scored as 0 = yes or 1 = no and then summed for a possible score of 0 to 13, with higher scores indicating worse enthesitis.

If 7 or more items are available, MASES will be imputed by dividing the sum score with the number of assessments and multiplying the result with 13. If less than 7 items are available, MASES will be treated as missing.

Presence of enthesitis at Baseline should be defined as a Baseline MASES score >0.

Summaries of MASES will be restricted to subjects with a MASES >0 at AS0008 Baseline.

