8.3 Statistical analyses of other efficacy variables

The following other efficacy variables will be summarized for the FAS at scheduled visits in accordance with the schedule of study assessments in [Table 2-1](#), by treatment group at completion of AS0008 and overall:

- ASAS40, ASAS20 and ASAS5/6 response at each visit in AS0009, relative to AS0008 Baseline.
 - Summaries will not be presented for individual components of the ASAS with the exception of PGADA which is a standalone endpoint.
- ASAS-PR response at each visit in AS0009, relative to AS0008 Baseline.
- Change from AS0008 Baseline in ASDAS-CRP at each visit in AS0009.
 - Summaries will not be presented for the individual components of the ASDAS-CRP with the exception of PGADA which is a standalone endpoint.
- ASDAS-ID at each visit in AS0009 (including Low Disease Activity, High Disease Activity and Very High Disease Activity categories).
- Change from AS0008 Baseline in BASDAI at each visit in AS0009.
- Change from AS0008 Baseline in BASFI at each visit in AS0009.
- Change from AS0008 Baseline in BASMI at each visit in AS0009.
- Change from AS0008 Baseline in MASES at each visit in AS0009.
 - Only subjects with MASES >0 at AS0008 Baseline will be included.
- Change from AS0008 Baseline in PGADA at each visit in AS0009.
- Change from AS0008 Baseline in TNSP at each visit in AS0009.
- Change from AS0008 Baseline in SF-36 PCS and MCS at each visit in AS0009.

- Change from AS0008 Baseline in SF-36 domain scores (Physical Functioning, Role Physical, General Health, Bodily Pain, Vitality, Social Functioning, Role Emotional and Mental Health) at each visit in AS0009.
- Change from AS0008 Baseline in ASQoL at each visit in AS0009.
- Change from AS0008 Baseline in HADS-A and HADS-D scores at each visit in AS0009.
- Incidence of depression and anxiety status “normal” as defined by HADS-A and HADS-D scores below 8 at each visit in AS0009
- Change from AS0008 Baseline (expressed as ratio to Baseline) in CRP at each visit in AS0009
 - For CRP the rules for handling values that are lower than the LLOQ identified in AS0008 will be followed as per [Section 8.1.12](#).

One set of summaries will be produced for all the above parameters using data following NRI or MI as appropriate, as described in Section [4.2.1](#).

For ASAS40, ASAS20, ASAS5/6 and BASDAI, an additional set of summaries will be produced using OC data.

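### MASES is summarized only for subjects with MASES >0 at AS0008 Baseline; the full-FAS summary in protocol 13.4 is dropped, and SAP 3.10 does not declare the departure

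*SAP*

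**What the plan says.** The protocol lists among its other objectives "To assess the impact on enthesitis" (3.3). The matching variable is "Change from Baseline of AS0008 in the MASES Index" (4.3.2, other efficacy variables). For the population, protocol 13.4 states: "Secondary and other efficacy variables will be summarized for all subjects in the FAS". It makes no exception for MASES.

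The SAP narrows this in four operative places:

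- Section 4.2.1, on the imputation: "Subjects with a MASES score of zero at AS0008 Baseline will be excluded prior to performing the procedure outlined below".
- Section 8.1.6: "Summaries of MASES will be restricted to subjects with a MASES >0 at AS0008 Baseline". The introduction to section 8 carries the same restriction.
- Section 8.3, under the MASES entry: "Only subjects with MASES >0 at AS0008 Baseline will be included".

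Section 8 also says: "Efficacy variables will be summarized and listed for the FAS". The restriction is worded for summaries, so the by-subject listings still cover the FAS.

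SAP 3.10, which collects the changes to protocol-defined analyses, does not mention MASES. The change appears in the Amendment 1 log (13.1.2) without a reason: "Summaries of MASES were restricted to subjects with enthesitis (MASES > 0) at AS0008 Baseline".

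**The concern.** A group chosen because a count is above its floor is followed for change on that same count, with no control arm. Part of any fall in such a group is regression to the mean and would appear without a drug effect. The subjects left out, those at 0, are the ones in whom only worsening can be observed, and no MASES summary describes them.

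At stake is how the enthesitis objective is read. The report would give a mean improvement among subjects who had enthesitis at the start, with no table showing how many of the others developed it over up to 204 weeks of treatment in AS0009. A reader who relies on protocol 13.4 and SAP 3.10 would take the mean to describe the FAS.

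**Working it through.** The plan gives no MASES figure and no formal sample size (protocol 13.10), so there is no planned number to reproduce. The direction follows from an identity. The size can only be illustrated.

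**Direction.** Let p be the share of the FAS with MASES >0 at AS0008 Baseline, R the mean change in that group, Z the mean follow-up score in the Baseline-zero group, and F the full-FAS mean change. MASES runs from 0 to 13 (protocol 10.6), so Z cannot be negative.

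- F = p × R + (1 - p) × Z, hence R = [F - (1 - p) × Z] / p.
- If F ≤ 0, then R ≤ F/p ≤ F. The restricted change is at least as favorable as the full-FAS change. No distributional assumption is needed.

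**Two parts of the gap.** Assume F = -1.5 and Z = 0.5:

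- p = 0.40: (-1.5 - 0.60 × 0.5) / 0.40 = -4.50
- p = 0.55: (-1.5 - 0.45 × 0.5) / 0.55 = -3.14
- p = 0.70: (-1.5 - 0.30 × 0.5) / 0.70 = -2.36
- p = 0.85: (-1.5 - 0.15 × 0.5) / 0.85 = -1.85

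At p = 0.70, dilution by zeros alone gives -1.5 / 0.70 = -2.14. The remaining -0.21 (0.30 × 0.5 / 0.70) comes from Baseline-zero subjects who score above 0 later. Dilution is only a change of denominator, so the whole gap should not be called bias.

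**Size with no true effect.** All inputs are assumed: two visits, lognormal-Poisson counts capped at 13, log-scale SD 1.5, 40% to 85% of subjects >0 at Baseline, and 50% to 90% of the log-scale variance stable within a subject. Counts are scaled to the maximum of 285 subjects (protocol 5.1.3).

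| Baseline >0 | Stable share | Change, all | Change, Baseline >0 | Relative change | Excluded of 285 | Of these, >0 at follow-up |
|---|---|---|---|---|---|---|
| 40% | 0.5 | 0.000 | -1.025 | -39.6% | 171 | 56 |
| 40% | 0.9 | 0.005 | -0.580 | -22.3% | 171 | 44 |
| 55% | 0.5 | 0.003 | -0.928 | -26.6% | 128 | 56 |
| 55% | 0.9 | 0.003 | -0.468 | -13.4% | 128 | 44 |
| 70% | 0.5 | -0.006 | -0.786 | -16.5% | 85 | 48 |
| 70% | 0.9 | 0.005 | -0.346 | -7.3% | 85 | 37 |
| 85% | 0.5 | 0.006 | -0.532 | -7.9% | 43 | 30 |
| 85% | 0.9 | 0.001 | -0.214 | -3.2% | 43 | 23 |

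The identity reproduces the first row: p = 0.401, Z = 0.686 and F = 0 give -0.599 × 0.686 / 0.401 = -1.025.

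A second model, beta-binomial over 13 sites with mean 2.5 and about 65% >0 at Baseline, gives -0.23 if disease is fully stable. If 40% of subjects have an independent enthesitis propensity at follow-up, it gives 0.6 × (-0.23) + 0.4 × (2.50 - 3.87) = -0.69.

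**Other planned outputs.** The SAP 8 sensitivity analyses on observed data do not include MASES. The post-entry summary of extra-articular manifestations in SAP 6.3 covers uveitis, IBD and psoriasis, not enthesitis. No other planned MASES summary includes the Baseline-zero subjects.

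**The case against.** A summary of the Baseline-positive group is reasonable in itself. Subjects at 0 cannot improve, and a mean over everyone mixes them into a change score. This stands as a reason to keep the table, but not as a reason to let it replace the one the protocol specifies.

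A reader might infer that new enthesitis becomes invisible, or that MASES is the only place it could show. The documents do not support that. The listings cover the FAS (SAP 3.1 and 8). Protocol 9.1.1 has disease signs recorded as adverse events if they change considerably or increase in a clinically significant manner, and protocol 9.5.3 has clinically significant changes on physical examination, which includes the musculoskeletal system, recorded as adverse events. Enthesitis is also one of the five BASDAI symptoms (SAP 8.1.4), and BASDAI is summarized on the full FAS. These routes are partial: listings are not summaries, milder enthesitis need not become an adverse event, and the BASDAI item stays inside a composite.

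Nor was the change concealed. It is stated in four operative sections and in the change log. What is missing is the entry in SAP 3.10, with a reason.

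The sizes are open to challenge. Baseline prevalence and visit-to-visit variability of MASES are not in the documents, and the larger simulated falls count real fluctuation of disease as well as measurement noise. AS0008 enrolled subjects with active AS, so uncontrolled change from its Baseline may contain some regression to the mean in the full FAS too. All of this stands; it leaves the direction intact and the size open.

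**Conclusion.** The point holds as a departure from protocol 13.4 that SAP 3.10 does not declare, with a known direction and an unknown size. The direction rests only on the floor of 0 and applies when the full-FAS mean change is zero or an improvement. The range of about -0.2 to -1.0 points without a true effect, and the 43 to 171 excluded subjects of whom 23 to 56 would score above 0 at follow-up, illustrate assumed inputs and are not estimates for this trial. It would go too far to say that the reported improvement is an artefact: the selection effect adds to whatever true effect exists, and part of the difference from the full-FAS mean is dilution.

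The consequence is limited. MASES is neither a primary nor a secondary variable, and no test or decision depends on it. The change should still be made, because the missing table is one the protocol specifies and the data are already collected.

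**What to change.** 1. In SAP 4.2.1, 8, 8.1.6 and 8.3, add the MASES summary for all FAS subjects (absolute value and change from AS0008 Baseline), with the imputation run on the same population.
2. Add a table of n (%) with MASES >0 at each visit by Baseline status (0 or >0), based on observed data. It should not use the imputed values: the SAP 4.2.1 model is multivariate normal, values outside 0 to 13 are reset to the limits, and no rounding is stated. A draw of 0.3 would count as enthesitis and inflate new onset.
3. Keep the Baseline >0 table as an additional display, labelled as a selected subgroup, and declare it with its reason in SAP 3.10.
4. While editing SAP 8.1.6, correct the item coding. It gives 0 for yes and 1 for no, yet says that higher scores mean worse enthesitis. Read literally, MASES >0 would select subjects with at least one unaffected site.

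The cost is SAP wording, one more imputation run and two tables. If enthesitis improves overall, the full-FAS mean change will be smaller than the restricted one.
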